4.2 Discussion of Study Design, Including the Choice of Control Group

This is an open-label extension study of Study HGT-SAN-093 intended to provide ongoing treatment with HGT-1410 during the treatment period to patients who received HGT-1410 in Study HGT-SAN-093 and to initiate treatment to patients who received no-treatment in Study HGT-SAN-093. As such, all patients will be treated during this study; there is no control group.

4.3 Method of Assigning Subjects to Treatment Group

Patients who were randomized to no-treatment in Study HGT-SAN-093 (Group 3) will be re-randomized in a 1:1 allocation ratio to receive Q2W or Q4W dosing (Groups 3A or 3B, respectively). To help ensure balance between the dose groups with respect to age at Baseline, the randomization will be stratified by age group (≤ 30 months and >30 months). Patients who were randomized to receive HGT-1410 in Study HGT-SAN-093 will remain on the same treatment regimen in Study SHP-610-201.

4.4 Blinding

This study will not be blinded.

4.5 Determination of Sample Size

As this is an extension study of Study HGT-SAN-093, any patients who enrolled and completed that study are eligible to enroll in Study SHP-601-201, and no statistical estimation for sample size calculation was performed. A maximum sample size of 21 patients in this study is expected based on the sample size in Study HGT-SAN-093.

5. EFFICACY AND SAFETY ENDPOINTS

5.1 Primary Endpoint

Safety is the primary objective of the study and will be assessed during the study by the following:

- Collection of adverse events (AEs; by type, severity, and relationship to treatment [HGT-1410, the IDDD, device surgical procedure, or IT administration process])
- Changes in clinical laboratory testing (serum chemistry, hematology, urinalysis)
- Physical examination
- Vital signs
- Twelve-lead electrocardiogram (ECG) recordings
- CSF laboratory parameters (including chemistries, cell counts)
- Anti-rhHNS antibodies in CSF and serum, including determination of antibodies having enzyme neutralizing activity

5.2 Secondary Endpoints

The secondary endpoints of this study are:

- The change from Baseline in BSID-III or KABC-II age-equivalent, DQ, and developmental delay scores
- The change from Baseline in adaptive behavioral function domains, assessed by VABS II, using raw scores, age-equivalent scores, and DQ scores
- The change from Baseline in total cortical grey matter volume, as assessed by MRI

5.3 Exploratory Endpoint(s)

5.4 Pharmacokinetic and Pharmacodynamic Endpoints

The pharmacokinetic endpoint is to determine the pharmacokinetic behavior of HGT-1410 in serum, based on the following parameters:

- Maximum concentration occurring at t_{max} (C_{max})
- Time of maximum observed concentration sampled during a dosing interval (t_{max})
- Area under the curve from the time of dosing to the last measurable concentration (AUC_{0-last})
- Area under the curve extrapolated to infinity, calculated using the observed value of the last non-zero concentration ($AUC_{0-\infty}$)
- First order rate constant associated with the terminal (log-linear) portion of the curve (λ_Z)
- Terminal half-life ($t_{1/2}$) calculated as $0.693/\lambda_Z$

- Total body clearance for extravascular administration divided by the fraction of dose absorbed (CL/F)
- Volume of distribution associated with the terminal slope following extravascular administration divided by the fraction of dose absorbed (Vz/F)

The pharmacodynamic endpoint is to determine the GAG concentrations in CSF and urine.

5.5 Health Status Endpoint

The health status endpoint is the ITQoL scores at each assessment time and the corresponding change from Baseline.

5.6 Health Economics and Outcomes Research Endpoint

The health economic and outcome research endpoints evaluate the key HCUQ variables, such as the number of emergency room visits, caregiver employment status (full-time [FT], part-time [PT], and not working [NW]), and the number of hours of additional paid help needed by caregivers, over the treatment period of the study.

6. EFFICACY AND SAFETY VARIABLES

6.1 Schedule of Evaluations

Please refer to Protocol SHP-610-201 amendment 2 for the Schedule of Events tables for Group 1 (patients who received HGT-1410 Q2W in Study HGT-SAN-093), for Group 2 (patients who received HGT-1410 Q4W in Study HGT-SAN-093), for Group 3A (patients who received no treatment in Study HGT-SAN-093 and are randomized to receive HGT-1410 Q2W in Study SHP-610-201), and for Group 3B (patients who received no treatment in Study HGT-SAN-093 and are randomized to receive HGT-1410 Q4W in Study SHP-610-201).

6.2 Efficacy Assessments

6.2.1 Neurocognitive and Developmental Assessments

The study methodology will include standardized neurodevelopmental assessments to provide a quantifiable measure of patient neurodevelopmental status (see [Table 1](#)). The assessments are estimated to last between 2 and 4 hours and must be conducted prior to any invasive procedures, such as blood draws, and prior to sedation or anesthesia. Neurodevelopmental status will be assessed over time by measuring cognitive and adaptive functions as follows:

- Cognition: The BSID-III (Bayley, 2005) will be used to assess all patients through the age of 42 months. Once patients reach age 42 months, an attempt will be made to switch the cognitive assessment to the KABC-II. If the cognitive status of the patient does not allow for testing by the KABC-II, the BSID-III may be used.
- Adaptive behaviors: The VABS-II (Sparrow, 2005) will be used to assess all patients.

For this study, outcome measures will be computed for each patient enrolled. The psychometric instruments are summarized below in [Table 1](#).

Table 1 Neurodevelopmental Assessments Tests

| Cognitive Test or Scale | Developmental or Cognitive Areas of Assessment |
|--------------------------|--|
| BSID-III | Summary score and sub-domains: - Cognitive - Motor - Social/Emotional - Language |
| KABC-II | Cognitive and processing skills |
| ADAPTIVE BEHAVIOR | |
| VABS-II | Communication Daily Living Socialization Motor Skills |

Abbreviations: BSID-III=Bayley Scales of Infant and Toddler Development, Third Edition; KABC-II= Kaufman Assessment Battery for Children, Second Edition; VABS-II=Vineland Adaptive Behavior Scales, Second Edition

6.2.2 Quality of Life Indicator: Infant Toddler Quality of Life Questionnaire

The ITQoL will be administered during the study. The ITQoL was developed for children at least 2 months of age up to 5 years and assesses the physical, mental, and social well-being of the child and assesses the quality of the parent/guardian's life. If a patient is over 5 years of age, they do not have to complete the ITQoL.

6.2.3 Health Economics and Outcomes Research: Healthcare Utilization Questionnaire

The HCUQ will be administered during the study. This HCUQ focuses on the direct and indirect costs of care for patients with MPS-III.

6.3 Magnetic Resonance Imaging

6.3.1 Head

Regional brain volumes, including total cortical gray matter volume, will be assessed through an MRI of the head. The patient will be under general anesthesia for this assessment. Instrument standardization and central analysis of MRIs will be performed by a designated contract research laboratory.

6.3.2 Liver and Spleen

Liver and spleen volumes will be assessed through an MRI, performed at the same times as for the MRI of the head. The patient will be under general anesthesia for this assessment. Instrument standardization and central analysis of MRIs will be performed by a designated contract research laboratory.

6.4 Pharmacokinetic Assessments

Blood samples will be collected for measurement of serum concentrations of HGT-1410 and determination of pharmacokinetic parameters at the times specified in the schedules of events in Protocol SHP-610-201. Additionally, CSF samples will be collected from patients who received no treatment in Study HGT-SAN-093 at the times specified in the schedules of events in Protocol SHP-610-201.

Patients may be discharged from the hospital after the 24-hour blood draw. Patients will either stay locally in a hotel or return home (if they live in close proximity to the hospital); this will be decided in consultation with the Investigator. Patients will return to the hospital for pharmacokinetic blood and CSF sampling at the 48-hour time point. Patients will be discharged to home after the physical examination and blood draws have been completed at the 48-hour PK time point. See Appendix 6 for more details regarding timing for pharmacokinetic sample collection.

6.5 Pharmacodynamic Biomarker Assessments (CSF and Urine GAG Levels)

CSF and urine samples will be obtained to measure the concentration of GAG according to the schedules of events in Protocol SHP-610-201.

6.6 Concomitant Medications, Therapies, and Medical/Surgical Interventions

All non-protocol treatments and medications that occur from the time of informed consent through the safety follow-up contact are regarded as concomitant and will be documented on the appropriate pages of the eCRF. Concomitant therapy includes any therapies/interventions administered to patients, and these will be recorded on the concomitant therapy eCRF. Any medical/surgical procedures performed on the patients will be recorded on the concomitant medical/surgical procedures eCRF. Concomitant medications, both prescribed and over-the-counter (including genistein and anesthesia medications) will be recorded on the concomitant medication eCRF.

Every effort should be made to keep symptomatic MPS IIIA treatment constant throughout the study. However, changes in medications are acceptable if necessary according to clinical judgment. All changes will be recorded on the appropriate eCRF. Concomitant medication will be coded using the World Health Organization-Drug Dictionary (WHO-DD).

6.7 Safety Assessments

6.7.1 Vital Signs

Vital signs are to be recorded on the eCRF for all patients and will include heart rate, blood pressure, respiration rate, and body temperature. Vital signs will be recorded for at least 4 hours following each dose of HGT-1410, as described in the schedules of events in Protocol SHP-610-201.

6.7.2 Physical Examination, Including Height, Weight, and Head Circumference

During the study, physical examinations will be performed at the time points indicated in the Schedules of Events. For Groups 1 and 2, full physical examinations will be conducted at Weeks 96, 120, 144, and 168, and for Groups 3A and 3B, full physical examinations will be conducted during the IDDD implantation period and at Weeks 24, 48, 72, 96, and 120. The remainder of physical examinations will be symptom-directed, including examinations during the safety follow-up period in patients who do not have the IDDD removed (partial or full device) at the end of the treatment period.

Physical examinations will include a review of the patient's general appearance, neurological examination, as well as evaluation of the body systems described in [Table 2](#), including the port and catheter track. Any abnormal change in findings will be recorded as an AE on the appropriate eCRF.

Table 2 Assessments for Physical Examinations

| Assessment | Assessment |
|-------------------------|-----------------|
| General appearance | Endocrine |
| Head and neck | Cardiovascular |
| Eyes | Abdomen |
| Ears | Genitourinary |
| Nose | Skin |
| Throat | Musculoskeletal |
| Chest and lungs | Neurological |
| Port and catheter track | |

Height and weight will be recorded for all patients.

The clinical site staff will be instructed to use calibrated scales for weight measurement where possible. The same scale is to be used at the clinical site for all patients at each specified time point during the study.

Head circumference will be measured for Groups 3A and 3B during the IDDD implantation period. All data will be recorded on the eCRF.

6.7.3 Electrocardiogram

An ECG will be performed in accordance with the clinical site's standard practice(s) and are to be performed after study drug administration. Electrocardiogram recordings will be read locally at the clinical site and will include an assessment of heart rate, sinus rhythm, atrial or ventricular hypertrophy, PR, QRS, and QT. Identification of any clinically significant findings and/or conduction abnormalities will be recorded on the eCRF. If the patient is unable to cooperate with

electrocardiography, and if sedation or general anesthesia is employed during that study visit, the ECG may be performed under sedation/anesthesia.

6.7.4 Clinical Laboratory Tests

Blood and urine samples will be collected as described in this section for clinical laboratory testing.

Clinical laboratory testing will only be performed when indicated for a device-related AE for patients who do not have the IDDD removed (partial or full device) at the end of the treatment period.

Clinical laboratory tests will include the laboratory tests presented for the HGT-SAN-093 CSR.

6.7.5 Cerebrospinal Fluid Assessments

Cerebrospinal fluid will be obtained from patients during surgical implantation of the IDDD (Groups 3A and 3B only), immediately prior to each injection of study drug and at the safety follow-up visit. Should the IDDD become clogged or undergo mechanical complications, the CSF sample will be obtained via LP.

The volume of CSF collected at each visit will vary according to the number of CSF assessments. The initial 1 mL of CSF aspirated via the IDDD will be discarded, to eliminate fluid in the device's "dead space." The next 1 mL of CSF will be sent to the local laboratory. Subsequently drawn CSF will be stored, depending on the requirement for that visit (see the schedules of events in Protocol SHP-610-201, and the Laboratory Manual). If CSF is obtained via LP, there is no need to discard the first mL of CSF, and this can be sent to the local laboratory for standard clinical assessments. If the patient is clinically stable in the opinion of the Investigator, HGT-1410 can be administered immediately following withdrawal of CSF, without awaiting the results of the CSF clinical laboratory data.

6.7.5.1 Standard CSF Safety Laboratory Assessments

An aliquot of each CSF sample collected will be evaluated for CSF standard chemistries, glucose, protein, and cell counts.

6.7.5.2 Anti-rhHNS Antibodies and Biomarkers in CSF and Serum

An aliquot of each CSF sample collected will be quick frozen for subsequent analysis of anti-rhHNS antibody evaluation, exploratory proteomics biomarkers, and/or other CSF biomarkers.

Blood samples will be collected and evaluated at Shire or Shire-designated laboratories for the determination of serum anti-rhHNS antibodies.

6.7.5.3 CSF GAG Levels and Biomarkers

An aliquot of each CSF sample collected will be quick frozen for subsequent analysis of CSF GAG. The CSF pharmacodynamic sample will be obtained as described in protocol Section 7.11.5.3.

6.7.5.4 [REDACTED]

6.7.6 Device Assessments

These data will be collected on the patient's eCRF from the time of initial implantation.

6.8 Adverse Events Assessments

Adverse events will be monitored continuously throughout the study.

For the purposes of this study, the period of observation extends from the time at which the patient, the patient's parent(s), or the patient's legally authorized representative gives informed consent until the patient's final evaluation of the study. For safety purposes, the final evaluation for the treatment period will be defined as the follow-up evaluation performed approximately 30 days after the last dose for patients who complete the study.

For a detailed definition on AEs, Serious AEs (SAEs), adverse events due to systemic exposure to HGT-1410, infusion/hypersensitivity reactions and management, IDDD-related adverse events, severity of AEs, and relatedness of AEs and SAEs, please refer to the SHP-610-201 Protocol Section 7.13.

7. STATISTICAL ANALYSIS

7.1 General Methodology

Statistical analysis will generally be performed by the Biometrics Department of Shire using SAS statistical software (SAS Institute, Cary, NC, USA). Analysis of any PK and health economics and outcomes data will be performed by the Shire Clinical Pharmacology and Pharmacokinetics group and the Health Economics and Outcomes Research groups, respectively. The analysis methods for all other study data (demographic and baseline characteristics, efficacy variables, and safety variables) will be detailed in this SAP.

Summary statistics for continuous variables will include the n, mean, standard deviation, median, minimum, and maximum. Categorical variables will be summarized in a contingency table by the frequency and percentage of patients in each category.

Unless otherwise indicated, all summary statistics will be presented by treatment groups (either Q2W or Q4W) to which the patients were randomly assigned (for patients who were initially assigned to Q2W or Q4W group in Study HGT-SAN-093 or patients who were assigned to no-treatment in HGT-SAN-093 and were randomly assigned to Q2W or Q4W in Study SHP-601-201).

No summary statistics and hypothesis testing will be presented for efficacy data. Instead, subject listings will be presented for the selected efficacy endpoints.

Data from Study HGT-SAN-093 will be combined with that of Study SHP-610-201 for analysis, for subjects who enrolled in SHP-610-201. The data included for treated patients in HGT-SAN-093 starts from the baseline of Study HGT-SAN-093 and for patients who received no treatment in HGT-SAN-093 from the baseline of Study SHP-610-201. Baseline is the assessment obtained prior to the first dose of HGT-1410.

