4. STUDY DESIGN

4.1 General Description

This is an open-label extension study of HGT-1410 for patients who completed through at least the Week 48 Visit in Study HGT-SAN-093. Patients who originally received HGT-1410 in Study HGT-SAN-093 will remain on the same dosing regimen as they received in Study HGT-SAN-093; Group 1 will receive HGT-1410 every 2 weeks (Q2W) and Group 2 will receive HGT-1410 every 4 weeks (Q4W). Patients in Groups 1 and 2 will begin treatment at Week 50 and Week 52, respectively, of this extension study (Study SHP-610-201). Patients who originally received no-treatment in Study HGT-SAN-093 (Group 3) will receive an IDDD following informed consent and will be re-randomized in a 1:1 allocation ratio to receive HGT-1410 via a Q2W or Q4W dosing regimen (Groups 3A and 3B, respectively) in Study SHP-610-201. Patients in Groups 3A and 3B will begin treatment on Week 0 of the extension study.

It is anticipated that the IDDD will be used to collect CSF samples and to deliver IT injections of HGT-1410 and preservative-free saline flushes. No other medication will be administered through the device. If the IDDD appears to be non-functional, or if its use is precluded on a scheduled day of dosing, site personnel will refer to the IDDD Manual, which provides details on the investigation and management of any IDDD-related issues. This includes possible partial revision or complete replacement of the IDDD as indicated. If the IT space is not accessible via the IDDD, study drug may be administered by LP. Should the IDDD become clogged, undergo mechanical complications or otherwise not be accessible, the CSF sample may also be obtained by LP. General anesthesia or sedation may be required for injections of study drug and some evaluations, and may be used at the discretion of the Investigator. The Data Monitoring Committee (DMC) will be notified of all IDDD failures and IDDD-related complications at times defined in the DMC charter.

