Patients should have the IDDD removed when they discontinue from or complete the treatment period of the study unless the investigator determines that it should not be removed based upon safety assessments. The device can remain in the patient (partial [catheter or suture wing only] or full [port, catheter, and suture wings]) if the patient is doing clinically well and there are no further known risk factors such as infection (eg, meningitis). The device may be partially or fully removed as medically required and determined by the neurosurgeon at a future date.

Safety and efficacy assessments will be performed at regular intervals over the approximate 2.5-year duration of the treatment period of the extension study. A pharmacokinetic sample for patients who received HGT-1410 in Study HGT-SAN-093 will be obtained at the Week 96 visit (after approximately 2 full years of exposure to HGT-1410 across Studies HGT-SAN-093 and SHP-610-201). Serum pharmacokinetic samples for patients who received no-treatment in Study HGT-SAN-093 will be obtained at the Week 0, 48, and 96, and CSF pharmacokinetic samples will be obtained on the Week 0 and 48 visits in Study SHP-610-201.

Patients who received HGT-1410 in Study HGT-SAN-093 will undergo a cumulative exposure to HGT-1410 for up to 42 months (168 weeks), whereas patients who received no treatment in Study HGT-SAN-093 will have a cumulative exposure to HGT-1410 for up to 30 months (120 weeks) in Study SHP-610-201.

Patients who do not have the IDDD removed (partial or full device) at the end of the treatment period will continue to be observed during a safety follow-up period with visits at the site every 6 months to evaluate patient safety of the device until the IDDD has been fully explanted.

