7.9 Analysis of Pharmacokinetic and Pharmacodynamic Data

7.9.1 Pharmacokinetic Measurement and Parameters

As the treatment period of the study was closed earlier than planned, there were few PK samples collected and hence no analysis on pharmacokinetic measurement and parameters will be provided.

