7.10 Analysis of Safety

7.10.1 Adverse Events

Once the patient has signed the informed consent form, AEs will be recorded throughout the study and at early termination. AEs will be coded using Medical Dictionary for Regulatory Affairs (MedDRA) version 17.1.

Treatment-emergent AEs, defined as all AEs from the time of initial IDDD implantation (or first dose if earlier) in either HGT-SAN-093 or SHP-610-201 to the data cut-off date, or 30 days after the date of last dose or 2 weeks after the date of device explant (whichever is later) if early termination, will be summarized. For each treatment group, the number and percentage of patients having an AE and the number of events, by system organ class (SOC) and preferred

term will be presented. Treatment-emergent AEs will also be summarized by severity and degree of relationship to study drug. In the case of multiple occurrences of the same AE (at the preferred term level) in an individual patient, the AE that is classified as the most severe (ie, maximum severity) will be identified for the analysis by severity and the AE that has the closest relationship to study drug/procedure will be identified for the analysis by relationship. In general, an AE will be considered a treatment-emergent AE if it cannot be definitively categorized otherwise by documentation that its onset preceded either IDDD surgery or first dose.

Serious adverse events will be similarly summarized by SOC and preferred term.

All treatment-emergent AEs, serious or life-threatening treatment-emergent AEs, treatment-emergent AEs leading to permanent discontinuation of study drug or resulting in death will be presented in a separate listing, respectively.

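### Each Q2W or Q4W adverse-event column mixes patients whose planned follow-up differs by about 48 weeks, and the SAP text plans no patient-time over the TEAE window

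*SAP*

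**What the plan says.** All references are to the interim SAP unless stated.

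- **Columns.** Section 7.1 summarizes by randomized regimen, so the Q2W column is Groups 1 + 3A and the Q4W column is Groups 2 + 3B. It adds that "Data from Study HGT-SAN-093 will be combined with that of Study SHP-610-201 for analysis, for subjects who enrolled in SHP-610-201". Parent-treated patients contribute from the HGT-SAN-093 baseline; the others enter "for patients who received no treatment in HGT-SAN-093 from the baseline of Study SHP-610-201".
- **Length of exposure.** Section 4.1 admits "patients who completed through at least the Week 48 Visit in Study HGT-SAN-093". Parent-treated patients "will undergo a cumulative exposure to HGT-1410 for up to 42 months (168 weeks"), while previously untreated patients "will have a cumulative exposure to HGT-1410 for up to 30 months (120 weeks) in Study SHP-610-201". Section 7.9.1 records the early stop: "As the treatment period of the study was closed earlier than planned".
- **AE window.** In 7.10.1 the TEAE window runs "from the time of initial IDDD implantation (or first dose if earlier"), in whichever of the two studies that occurred. It ends at the data cut-off or, for early termination, at the later of 30 days after the last dose and 2 weeks after explant. The addendum (section 2) gives the cut-off as 28 June 2017 and labels it as treatment period.
- **AE output.** Section 7.10.1 plans "the number and percentage of patients having an AE and the number of events" by SOC and preferred term, with further summaries by severity and relationship.
- **Time summaries.** Section 7.7 summarizes first-to-last-dose time in weeks.
- **Safety follow-up.** Section 8.1 leaves information from that period to the final SAP. The addendum (6.5.1) says that device-related AEs were recorded during it.

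**The concern.** Long-term safety is the primary objective, and 8.1 keeps summary statistics only for baseline characteristics, exposure and adverse events. The AE tables are therefore the main summary of the primary objective.

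A percentage of patients with at least one event depends on how long each patient was watched. Here one column averages over two cohorts with clearly different follow-up. The text plans no patient-time, rate or split by origin that would let a reader see this. The duration in 7.7 cannot stand in fully, because it leaves out the time from implantation to first dose and all time after the last dose, both of which the TEAE window can include.

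A second, separate gap concerns the end of the window. A patient who finishes treatment but keeps a full or partial device stays in the study. Read literally, 7.10.1 counts that patient to the data cut-off. If only device-related AEs were being recorded by then, the patient would be counted through time in which other AEs could not appear. That would matter directly once patient-years are used as a denominator.

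**Working it through.** **1. The plan's own figures.** Section 4.1 gives 168 and 120 weeks. 168 − 120 = 48 weeks, which matches the Week 48 entry requirement (48 + 120 = 168). The month labels reproduce at 4 weeks per month: 42 × 4 = 168 and 30 × 4 = 120.

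**2. Follow-up ratio within a column.** Let E be the extension weeks actually run. Groups 3A/3B have E and Groups 1/2 have E + 48.
- Planned maximum, E = 120: 168/120 = 1.40.
- E = 48 (assumed): 96/48 = 2.00.

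The lead is fixed, so early closure widens the ratio. The SAP does not say how many extension weeks were reached.

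**3. What this does to a percentage.** With a constant rate r per year, P(at least one event) = 1 − exp(−rT), where T = weeks × 7/365.25. So 48, 96, 120 and 168 weeks are 0.920, 1.840, 2.300 and 3.220 years. The rates are assumptions, and dosing time serves as a proxy for the TEAE window, whose dates the SAP does not give.

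| r per year | E = 48: Groups 1/2 against 3A/3B | E = 120: Groups 1/2 against 3A/3B |
|---|---|---|
| 0.05 | 8.8% against 4.5% | 14.9% against 10.9% |
| 0.2 | 30.8% against 16.8% | 47.5% against 36.9% |
| 0.5 | 60.1% against 36.9% | 80.0% against 68.3% |

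For example, at r = 0.2 and E = 48: 1 − exp(−0.2 × 1.840) = 0.308 and 1 − exp(−0.2 × 0.920) = 0.168. An assumed column of 7 + 4 patients would display (7 × 0.308 + 4 × 0.168)/11 = 25.7%, which describes neither cohort.

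**4. Q2W against Q4W.** The contrast depends only on how the cohort mix differs between columns. The splits are assumed; r = 0.2 and E = 48:
- 7 + 3: (7 × 0.308 + 3 × 0.168)/10 = 26.6%. Against 7 + 4 (25.7%) the gap is 0.9 points.
- 7 + 3 against 5 + 4: (5 × 0.308 + 4 × 0.168)/9 = 24.6%, a gap of 2.0 points.
- Over r = 0.2 and 0.5 and E = 48 and 120, these two comparisons span 0.7 to 3.4 points.
- A more uneven case, 7 + 2 against 5 + 5: (7 × 0.308 + 2 × 0.168)/9 = 27.7% against (5 × 0.308 + 5 × 0.168)/10 = 23.8%, a gap of 3.9 points.

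One patient is 1/11 = 9.1 to 1/9 = 11.1 points in columns of 9 to 11, so these differences are smaller than one patient.

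**5. What the fix would display.** With assumed parent arms of 7/7/7, all enrolled, Group 3 split 4/3, and full planned exposure:
- Q2W: (7 × 168 + 4 × 120) × 7/365.25 = 31.7 patient-years.
- Q4W: (7 × 168 + 3 × 120) × 7/365.25 = 29.4 patient-years.

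**6. End of the window, side by side.** Section 7.10.1 runs to the data cut-off unless there was early termination. Section 8.1 defers safety follow-up information. The addendum labels the cut-off as treatment period (section 2) and describes recording of device-related AEs in follow-up (6.5.1). No sentence says which end applies to a patient who completed treatment, kept the device and was in follow-up at the cut-off.

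**The case against.** The strongest case against is that this is descriptive output in at most 21 patients. No test or error rate is touched, and any cumulative percentage grows with follow-up. Section 7.7 already gives doses, duration and compliance by regimen, and the listings let a reader rebuild each patient's course. The table shells are not at hand and may show more. A rate is no cure either: if events cluster near implantation, it falls as follow-up lengthens. With an assumed 1.0 per year for 12 weeks and then 0.1, it is (12 + 0.1 × 84)/96 = 0.21 per year over 96 weeks and (12 + 0.1 × 156)/168 = 0.16 over 168. All of this stands, and it limits the weight of the point. It does not remove the gap between 7.7 and the TEAE window.

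Four stronger readings are tempting but not supported:

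- *The cohorts have no common time origin.* Section 7.10.1 starts every patient at first implantation or first dose, in whichever study that fell. Only the length of follow-up differs.
- *The regimen comparison is biased.* Group 3 is re-randomized 1:1, and the illustrated gaps are below one patient.
- *Section 6.8 contradicts 7.10.1.* Its evaluation about 30 days after last dose closes the treatment-period observation for completers; it does not define the TEAE window. The real tension is between 7.10.1 and the handling of safety follow-up.
- *Parent-study patients who did not roll over are wrongly left out.* They lie outside the safety population in 7.2, which requires an implant or a dose in the extension.

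On collection during follow-up, the addendum also plans an any-AE row. The loss of non-device AEs after treatment is therefore a possibility to settle, not an established fact.

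**Conclusion.** The point holds as a cheap improvement to descriptive safety output. Within each regimen column, planned follow-up differs by 48 weeks (168 against 120, ratio 1.40), and the ratio widens with early closure, to 2.0 at an assumed 48 extension weeks. At an assumed constant 0.2 events per year this separates the cohorts by 14.0 points at 48 extension weeks (30.8 − 16.8) and by 10.6 points at the planned maxima (47.5 − 36.9). A pooled percentage should therefore not be read as an absolute long-term risk without the patient-time behind it. Counts, listings and the Q2W against Q4W contrast remain usable.

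The 48-week difference comes from the SAP. The percentages rest on assumed rates, cohort sizes and extension length, on a constant hazard, and on dosing time as a proxy for the TEAE window. That no patient-time is planned is judged from the SAP text only. The unclear window end for patients who keep a device is a separate, smaller point that needs one sentence whatever is decided about rates.

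**What to change.** In section 7.10.1 of the interim SAP:

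- (a) Add total patient-years over the TEAE window, and events per patient-year, by regimen, to the overall TEAE, SAE and related-AE rows. Count from the reference date already defined in 7.10.6 to the end of the TEAE window. Leave the SOC and preferred-term rows as they are.
- (b) State which window end applies to patients who enter safety follow-up with a full or partial device. For non-device AEs, stop the clock when their collection ended.
- (c) Optionally, show patient-years and the overall TEAE and SAE rows by origin, Groups 1/2 against Groups 3A/3B.

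The cost is a few sentences and a few extra cells, from dates already collected. The downsides are sparse cells in at most 21 patients, and a single rate that assumes a roughly constant hazard. Patient-years should therefore be shown beside every rate.
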